#### 6.0 **DOSE MODIFICATIONS FOR ADVERSE EVENTS**

#### The Study Chair must be notified of any dosage modification or use of myeloid growth factor.

#### 6.1 **Dose Modifications for Day 15 Dosing due to Toxicity on Day 15**

#### 6.1.1 Hematologic Toxicity

- 6.1.1.1 Patients who have Grade 4 neutropenia or Grade 3 thrombocytopenia (platelets < 50,000/mm^3) on Day 15 will have their dose withheld. If the toxicity resolves to ANC  $\geq$  500/mm^3 and platelets  $\geq$  50,000/mm^3 (transfusion independent) by Day 18, the dose may be given. If the toxicity does not resolve to ANC  $\geq$  500/mm^3 and platelets  $\geq$  50,000/mm^3 by Day 18, the dose will be omitted and this will be considered a DLT. Patients should receive subsequent cycles of drug per Section 6.2. Patients who require that their Day 15 dose be omitted for Grade 4 neutropenia or Grade 3 platelets (< 50,000/mm^3) after two dose reductions must be removed from protocol therapy.
- 6.1.1.2 Patients who meet hematological DLT criteria as defined in Section 5.5.2.1 on Day 15 will have their Day 15 dose omitted. Patients should receive subsequent cycles of drug per Section 6.2 after their toxicity resolves, no sooner than the planned start of the subsequent cycle. Patients

nstitute of the National Institutes of Health

who require that their Day 15 dose be omitted for hematologic DLT as defined in Section 5.5.2.1 after two dose reductions must be removed from protocol therapy.

**ADVL1515** 

#### 6.1.2 Non-Hematologic Toxicity

- 6.1.2.1 Patients who have Grade 3 or Grade 4 non-hematological toxicity attributable to the study drug **prior to** the Day 15 dose (with the exception of the DLT exclusions in Section 5.5.1.1) will be considered to have had a DLT. If the toxicity resolves to meet eligibility or  $\leq$  Grade 2 (if not part of eligibility criteria) by Day 15, the dose may be given but at the next lower dose level.
- 6.1.2.2 Patients who have Grade 3 or Grade 4 non-hematological toxicity attributable to the study drug **on** Day 15 prior to dosing (with the exception of the DLT exclusions in Section 5.5.1.1) will have their dose withheld and this will be considered a DLT. If the toxicity resolves to meet eligibility or  $\leq$  Grade 2 (if not part of eligibility criteria) by Day 18, the dose may be given but at the next lower dose level. If the toxicity does not resolve by Day 18, the dose will be omitted. Patients should receive subsequent cycles of drug but with dose modifications according to Section 6.3.

#### 6.2 **Dose Modifications for Hematological Toxicity**

- 6.2.1 Patients who have dose-limiting thrombocytopenia should receive subsequent cycles at the next lower dose level.
- 6.2.2 Patients who have dose-limiting neutropenia with no other dose-limiting toxicity should receive the same dose in the next cycle with myeloid growth factor support. [Note: Patients MUST NOT receive prophylactic myeloid growth factor in the first cycle of therapy (See Section 7.4).] If dose-limiting neutropenia recurs after myeloid growth factor is added, then the patient should be given the next lower dose level for subsequent cycles. If dose-limiting neutropenia recurs in a patient that has received a dose level reduction but has not received myeloid growth factor, then myeloid growth factor should be administered. Patients who experience dose-limiting neutropenia after the addition of myeloid growth factor and one dose reduction must be removed from protocol therapy.
- 6.2.3 Patients who meet hematological DLT criteria as defined in Section 5.5.2.1 on Day 15 and have their Day 15 dose omitted will begin the subsequent cycle at the planned start of that cycle, if their toxicity has resolved.
- 6.2.4 Patients who experience dose-limiting thrombocytopenia after two dose reductions or dose-limiting neutropenia after addition of myeloid growth factor and one dose reduction must be removed from protocol therapy.
- 6.2.5 Patients who have a dose-limiting hematological toxicity that does not resolve to eligibility parameters within 21 days after the planned start of the next treatment cycle must be removed from protocol therapy.

6.2.6 No dose reduction beyond dose level 0 is allowed.

#### 6.3 **Dose Modifications for Non-Hematological Toxicity**

- 6.3.1 Patients who have any dose-limiting non-hematological toxicity (as defined in Section 5.5.1) may continue on protocol therapy upon meeting eligibility lab requirements or baseline but should receive subsequent doses at the next lower dose level.
- 6.3.2 If the same non-hematological dose-limiting toxicity recurs after one dose reduction, the patient must be removed from protocol therapy.
- 6.3.3 Patients who have a dose-limiting non-hematological toxicity that does not resolve to baseline or eligibility within 21 days after the planned start of the next treatment cycle must be removed from protocol therapy.
- 6.3.4 No dose reduction beyond dose level 0 is allowed.
- 6.3.5 Infusion Reactions: Patients experiencing an infusion reaction should be treated as per institutional guidelines. For subsequent infusions, premedication with diphenhydramine 0.5-1 mg/kg (max 50 mg) and/or other premedications may be considered at investigators discretion. The infusion rate may also be decreased by 50%. Patients should be monitored for signs and symptoms of infusion reactions with subsequent infusions.

#### 7.0 SUPPORTIVE CARE AND OTHER CONCOMITANT THERAPY

#### 7.1 **Concurrent Anticancer Therapy**

Concurrent cancer therapy, including chemotherapy, radiation therapy, immunotherapy, or biologic therapy may NOT be administered to patients receiving study drug. If these treatments are administered the patient will be removed from protocol therapy.

#### 7.2 **Investigational Agents**

No other investigational agents may be given while the patient is on study.

#### 7.3 Supportive Care

Appropriate antibiotics, blood products, antiemetics, fluids, electrolytes and general supportive care are to be used as necessary. See Section 4.2.2.5 for drugs that should not be used concomitantly due to potential interactions with LY2606368. Drugs that prolong the QTc may be used only if the drug is necessary and no alternatives are available. See Appendix IV for drugs that may prolong the QTc.

#### 7.4 **Growth Factors**

Growth factors that support platelet or white cell number or function can only be administered in accordance with Section 6.2.2 or for culture proven bacteremia or invasive fungal infection. G-CSF may be used only after completion of cycle 1 and may be given 24 hours after the administration of the dose on day 1 and day 15. G-CSF administration must be stopped 7 days prior to initiation of the subsequent cycle.

The Study Chair should be notified before growth factors are initiated.

#### 7.5 **Concomitant Medications**

- 7.5.1 Drugs that prolong the QTc may be used only if the drug is necessary and no alternatives are available. See Appendix IV for drugs that may prolong the QTc.
- 7.5.2 Sensitive CYP1A2 substrates (alosetron, caffeine, duloxetine, melatonin, ramelteon, tasimelteon, theophylline, tizanidine) may be used, but should be recorded as concomitant medications.

#### 8.0 EVALUATIONS/MATERIAL AND DATA TO BE ACCESSIONED

#### 8.1 Required Clinical, Laboratory and Disease Evaluation

All clinical and laboratory studies to determine eligibility must be performed within 7 days prior to enrollment unless otherwise indicated. Laboratory values used to assess eligibility (see Section 4.0) must be no older than seven (7) days at the start of therapy. Laboratory tests need **not** be repeated if therapy starts **within** seven (7) days of obtaining labs to assess eligibility. If a post-enrollment lab value is outside the limits of eligibility, or laboratory values are older than 7 days, then the following laboratory evaluations must be re-checked within 48 hours prior to initiating therapy: CBC with differential, bilirubin, ALT (SGPT) and serum creatinine. If the recheck is outside the limits of eligibility, the patient may not receive protocol therapy and will be considered off protocol therapy. Imaging studies, bone marrow aspirate and/or biopsy, must be obtained within 14 days prior to start of protocol therapy (repeat the tumor imaging if necessary).

STUDIES TO BE OBTAINED	Pre- Study	During Cycle 1	Prior to Subsequent Cycles^
History	Х	Weekly	Х
Physical Exam with vital signs	Х	Weekly	Х
Neurologic Exam	Х		Х
Height, weight, BSA	Х		Х
Performance Status	Х		
CBC, differential, platelets	Х	Twice Weekly	Weekly 
_		(every 3 to 4 days) 	
Pharmacokinetics 	Х	X	
Electrolytes including Ca 2+ , PO 4  , Mg 2+	Х	Weekly	Х
Creatinine, ALT, bilirubin	Х	Weekly	Х
Albumin	Х		Х
Tumor Disease Evaluation	X	End of Cycle 1	Every other cycle x 2 then q 3 cycles 
Bone Marrow Evaluation 	X	X	Every other cycle x 2 then q 3 cycles 
Pregnancy Test 	Х		
ECHO or gated radionuclide study	Х		
EKG 	Х	X	X 
Tumor Tissue Submission 	Х		
Correlative Biology Studies (optional) 	Х	X	

Institute of the Natio

THIS PROTOCOL IS FOR RESEARCH PURPOSES ONLY, SEE PAGE 1 FOR USAGE POLICY

- Studies may be obtained within 72 hours prior to the start of the subsequent cycle, unless otherwise specified within the table.
- 1 See Section 8.3 for timing and details of pharmacokinetic (PK) studies.
- 2 Women of childbearing potential require a negative pregnancy test prior to starting treatment; sexually active patients must use an acceptable method of birth control during the study and for 3 months after participation in this study. Abstinence is an acceptable method of birth control.
- 3 If patients have Grade 4 neutropenia then CBCs should be checked at least every other day until recovery to Grade 3 or until meeting the criteria for dose-limiting toxicity.
- 4 If patients develop Grade 4 neutropenia then CBCs should be checked every 3 to 4 days until recovery to Grade 3
- 5 Tumor Disease Evaluation should be obtained on the next consecutive cycle after initial documentation of either a PR or CR. Subsequent scans may restart 2 cycles after the confirmatory scan. Please note that for solid tumor patients, if the institutional investigator determines that the patient has progressed based on clinical or laboratory evidence, he/she may opt not to confirm this finding radiographically.
- 6 If a solid tumor patient is suspected to have or has a history of bone marrow involvement then a prestudy bone marrow biopsy and/or aspirate is required. This should then be repeated with each tumor disease evaluation.
- 7 See Section 8.4 for details regarding tumor tissue submission for the required and optional studies. If tissue blocks or slides are unavailable, the study chair must be notified prior to study enrollment.
- 8 See Section 8.5 for timing and details regarding correlative biology studies.
- 9 EKGs to be performed at baseline, and then immediately prior to and one hour after each infusion of LY2606368 is complete for the first 2 cycles. For subsequent cycles, EKGs are to be obtained as clinically indicated.

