#### 5.5.1 Non-hematological dose-limiting toxicity

5.5.1.1 Any Grade 3 or greater non-hematological toxicity attributable to the investigational drug with the specific exclusion of:

- Grade 3 nausea and vomiting < 3 days duration
- Grade 3 liver enzyme elevation, including ALT/AST/GGT, that returns to Grade ≤ 1 or baseline prior to the time for the next treatment cycle. Note: For the purposes of this study the ULN for ALT is defined as 45 U/L and the ULN for AST is defined as 50 U/L. Adverse event grades will be based on increases above the upper limit of normal, regardless of the subject's baseline. See Appendix IX for values that represent thresholds between CTCAE grades.
- Grade 3 fever
- Grade 3 infection

nstitute of the National Institutes of Health

This protocol is for research purposes only, see page 1 for usage policy

- Grade 3 hypophosphatemia, hypokalemia, hypocalcemia or hypomagnesemia responsive to supplementation.
- 5.5.1.2 Non-hematological toxicity that causes a delay of  $\geq$  14 days between treatment cycles.
- 5.5.1.3 Note: Allergic reactions that necessitate discontinuation of study drug will not be considered a dose-limiting toxicity.

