# **APPENDIX IX: TOXICITY-SPECIFIC GRADING**

# Bilirubin

Grade 1:	≤ 1.5X
Grade 2:	> 1.5X- 3X
Grade 3:	> 3X-10X
Grade 4:	> 10X

ALT: For the purpose of this study, the ULN for ALT is 45 U/L regardless of baseline.

Grade 1:	≤ 135
Grade 2:	136-225
Grade 3:	226-900
Grade 4:	> 900

AST: For the purpose of this study, the ULN for AST is 50 U/L regardless of baseline.

Grade 1:	≤ 150
Grade 2:	151-250
Grade 3:	251-1000
Grade 4:	> 1000

GGT:

Grade 1:	≤2.5X
Grade 2:	> 2.5X- 5X
Grade 3:	> 5X-20X
Grade 4:	> 20X

Institute of the National Institutes of Health

ADVL1515 THIS PROTOCOL IS FOR RESEARCH PURPOSES ONLY, SEE PAGE 1 FOR USAGE POLICY

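### AST and GGT elevations can be dose-limiting, but the required schedule measures neither, so these DLTs are found only where a site happens to test

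*Combined protocol and SAP*

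**What the plan says.** **DLT definition (Section 5.5.1.1).** The general rule counts "Any Grade 3 or greater non-hematological toxicity attributable to the investigational drug with the specific exclusion of" a short list of exceptions. One exception is "Grade 3 liver enzyme elevation, including ALT/AST/GGT, that returns to Grade ≤ 1 or baseline prior to the time for the next treatment cycle". The note to that exception fixes the ALT limit at 45 U/L, adds that "the ULN for AST is defined as 50 U/L", and says that "Adverse event grades will be based on increases above the upper limit of normal, regardless of the subject's baseline".

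**Grading (Appendix IX).** AST has its own table, under the statement "For the purpose of this study, the ULN for AST is 50 U/L regardless of baseline". GGT has a table in multiples of the upper limit, with no numerical limit given.

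**What is measured (Section 8.1).** The table of required studies has one row for liver enzymes, "Creatinine, ALT, bilirubin", taken pre-study, weekly in Cycle 1 and before later cycles. Albumin is taken pre-study and before later cycles. None of the footnotes adds AST or GGT.

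**Use of the DLT count (Sections 11.2 and 11.3).** The MTD is the highest dose with fewer than one-third of patients having a Cycle 1 DLT. Two or more DLTs in a cohort of up to six mean that the MTD has been exceeded, subject to an exception in Section 11.2.2.

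**The concern.** The DLT definition names three enzymes, and the schedule measures one of them. A patient can follow every required study, have an AST or GGT elevation that meets the definition, and be recorded as evaluable without DLT because nobody was asked to look. Another patient with the same elevation, at a site whose routine panel includes these enzymes, would be recorded as a DLT.

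The DLT count drives a primary aim, and the decision for a full cohort turns on one DLT versus two. Even an uncommon ascertainment gap therefore deserves closing if that is cheap. Failure to test also errs in one direction: it can remove a DLT from the count but cannot add one, so it favours escalation.

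**Working it through.** No figure in the plan is in dispute, so the check is mainly a comparison of sections.

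**1. Which AST and GGT events are DLTs.** All must be attributable to the drug.
- Grade 4: DLT whether or not it recovers, because the exception covers Grade 3 only.
- Grade 3, not back to Grade 1 or lower or to baseline before the next cycle: DLT.
- Grade 3 that does return in time: not a DLT.

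**2. Whether the AST grading is deliberate.** Appendix IX divides AST at 150, 250 and 1000 U/L. With the limit of 50 U/L, 3 × 50 = 150, 5 × 50 = 250 and 20 × 50 = 1000. The ALT cut-offs use the same multiples of 45: 135, 225 and 900. The AST table is consistent with the DLT note and does not look like a leftover.

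**3. Where a value could come from.**

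| Section | Liver tests required | AST or GGT? |
|---|---|---|
| 4.1.7.3 eligibility | bilirubin, ALT, albumin | no |
| 4.0 and 8.1 recheck before therapy | bilirubin, ALT | no |
| 8.1 schedule, pre-study | ALT, bilirubin, albumin | no |
| 8.1 schedule, weekly in Cycle 1 | ALT, bilirubin | no |
| 8.1 schedule, before later cycles | ALT, bilirubin, albumin | no |
| 11.2.1 evaluability for DLT | suitable monitoring, not itemised | not stated |

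The only other mention of AST is in Section 13.1, among Grade 1 and 2 events exempt from expedited reporting. That requires no test.

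**4. Comparison with other DLT criteria.** The electrolyte exceptions in Section 5.5.1.1 are matched by weekly electrolytes, with calcium, phosphate and magnesium named. The neutropenia-duration criterion is matched by more frequent blood counts (Section 8.1, footnote 3). The enzyme criterion stands out because it names analytes that the schedule leaves out, which suggests an oversight.

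**5. What still works without a scheduled test.** If a site has a local value, it can be graded. A missing baseline removes only one route to the recovery exemption; return to Grade 1 or lower remains. Sections 6.3.1 and 6.3.3 also refer to eligibility or baseline values, and neither is set for AST or GGT.

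**6. How the count could move (illustration only).** The documents give no rate for DLTs visible only through AST or GGT. Let *a* be the rate of all other DLTs and *b* the rate of AST/GGT-only DLTs among patients with no other DLT. Both are assumed. With full testing, p = a + (1 − a)b; with no testing, p = a. For six patients,

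P(2 or more DLTs) = 1 − (1 − p)^6 − 6p(1 − p)^5.

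| a | b | p, tested | P, tested | P, not tested |
|---|---|---|---|---|
| 10% | 2% | 0.118 | 0.151 | 0.114 |
| 10% | 5% | 0.145 | 0.212 | 0.114 |
| 20% | 2% | 0.216 | 0.384 | 0.345 |
| 20% | 5% | 0.240 | 0.442 | 0.345 |

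At *b* = 2% the probability falls by about 0.04 when nobody is tested (0.151 − 0.114 = 0.037; 0.384 − 0.345 = 0.039). At *b* = 5% it falls by about 0.10 (0.098 and 0.097). If some sites test, the loss lies in between. The sum treats all cohorts as six patients, although the rolling six can escalate sooner. It shows direction, not the expected size.

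**The case against.** The strongest reply is that AST and GGT are named inside an exception to an open-ended rule. That rule covers many toxicities with no scheduled test, which count when they are detected. On this view Appendix IX only says how to grade a value that exists, and the monitoring panel is a matter of choice. This is fair as a reading of the wording. It does not remove the gap: for laboratory events that cause no symptoms, detection depends on testing, and the plan has taken the trouble to define grades and a recovery test for these two.

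The reply is stronger on size. ALT and bilirubin are checked weekly in Cycle 1, so what is missed is a Grade 4 or unrecovered Grade 3 AST or GGT elevation without a qualifying ALT or bilirubin change. The adult data in Section 2.3.1 list no hepatic event among the common related non-hematologic ones, and Section 2.2.2 expects dose-limiting effects in other organ systems. The agent information in Section 9 is not available in the public text, so it cannot be checked for a hepatic signal.

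A reader might infer four stronger things that the documents do not support.
- *The rule cannot be applied at all.* It can, wherever a local value exists. Once an elevation is reported as an adverse event, Section 13.4.4 also asks for a resolution date or a record that it is ongoing.
- *Any Grade 3 or higher elevation is excused on recovery.* The exception is for Grade 3 only.
- *Dose cohorts become non-comparable.* The schedule is the same at every dose level, and nothing shows that local testing differs by cohort.
- *One additional DLT always turns an escalation into an exceeded MTD.* Section 11.2.2 allows expansion to 12 patients to be considered when two DLTs in six are of different classes and its other conditions are met. Its own example pairs liver toxicity with myelosuppression.

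**Conclusion.** The mismatch is real and narrow. Sections 5.5.1.1 and 8.1 and Appendix IX do not agree on which enzymes matter. As written, a patient can satisfy every scheduled study and be counted as DLT-free with an event that the plan defines as a DLT. The rule can be applied locally but not uniformly.

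Failure to test can only under-count DLTs. The amount cannot be derived from the documents, since the rate of AST/GGT-only DLTs is not given, and the illustrative probabilities rest entirely on assumed rates. Weekly ALT and bilirubin make a small effect the likely one. That sites differ in what they test is an inference from the absence of any required or central AST or GGT measurement; the plan does not state it. This is a low-cost improvement to the ascertainment of a primary endpoint and does not threaten the design.

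**What to change.** Reconcile Sections 5.5.1.1 and 8.1 and Appendix IX so that every enzyme in the DLT rule is measured when the rule needs it. The simplest change is to add AST and GGT to the existing creatinine, ALT and bilirubin row, at the same times: pre-study, weekly in Cycle 1 and before later cycles. This supplies the baseline, the Cycle 1 values and the recovery value from the same blood draw. State also which upper limit applies to GGT, since Appendix IX gives only multiples.

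The cost is two more analytes on samples already taken, with no extra visit or draw. Whether to change the DLT definition instead is the sponsor's decision.

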#### 4.1.7.3 Adequate Liver Function Defined as:

- Bilirubin (sum of conjugated + unconjugated) ≤ 1.5 x upper limit of normal (ULN) for age regardless of baseline.
- SGPT (ALT)  $\leq$  135 U/L (3x ULN). For the purpose of this study, the ULN for SGPT is 45 U/L regardless of baseline.
- Serum albumin  $\geq 2 \text{ g/dL}$ .

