#### 5.2 Criteria for Starting Subsequent Cycles

A cycle may be repeated every 28 days if the patient has at least stable disease and has again met laboratory parameters as defined in the eligibility section, Section 4.0.

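### After Cycle 1 no chemistry is scheduled before the Day 15 infusion, although the Day 15 dosing rule in Section 6.1.2 can turn on a laboratory toxicity

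*Combined protocol and SAP*

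**What the plan says.** The Section 8.1 table has one column for the time after Cycle 1, and it is a pre-cycle column. The electrolyte row and the creatinine, ALT and bilirubin row are weekly during Cycle 1 and carry a single mark in that later column. The note to the column states: "Studies may be obtained within 72 hours prior to the start of the subsequent cycle, unless otherwise specified within the table". Two rows do specify otherwise: the CBC stays weekly, and EKGs surround each infusion through Cycle 2. No footnote adds a mid-cycle chemistry.

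Section 5.1 gives the drug on Days 1 and 15 of each cycle, for up to 13 cycles, and refers the decision to delay or omit Day 15 to Section 6.1. Under 6.1.2.2, patients with attributable Grade 3-4 non-hematologic toxicity on Day 15 "will have their dose withheld and this will be considered a DLT". If the toxicity recovers by Day 18, to eligibility values or to Grade 2 or lower, the dose may follow one level down; otherwise it is omitted. Section 6.1.2.1 also requires the lower level when the toxicity came and resolved before Day 15. Section 6.3.1 says that patients with a non-hematologic DLT "may continue on protocol therapy upon meeting eligibility lab requirements or baseline but should receive subsequent doses at the next lower dose level".

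The only laboratory gate in later cycles is Section 5.2: a cycle may be repeated if the patient has at least stable disease and "has again met laboratory parameters as defined in the eligibility section".

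**The concern.** Section 6.1.2 has two kinds of trigger. Overt toxicity would ordinarily be noticed when the child attends for the infusion. A silent laboratory abnormality would not. Examples that Section 5.5.1.1 does not exclude are Grade 3 bilirubin or creatinine, Grade 4 ALT, and electrolyte abnormalities that are Grade 4, or Grade 3 and unresponsive to supplementation. After Cycle 1 the hematologic Day 15 rule keeps its weekly CBC, while the non-hematologic rule has no scheduled laboratory input. A site that follows the visible schedule exactly could give a full Day 15 dose to a child who already meets the protocol's own withholding rule. The same holds for a patient with a laboratory DLT in Cycle 1 who recovered and continued one level lower: that patient's chemistry also drops to once per cycle, although 6.3.2 requires removal if the same toxicity recurs.

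**Working it through.** The plan states no figure on this point, so the check is a reading of the schedule plus simple arithmetic.

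**Does the Day 15 rule apply after Cycle 1?** Section 6.1.2 does not say, so this is an inference.
- Section 5.1 sends Day 15 decisions to Section 6.1 without limiting them to one cycle.
- The hematologic rule in 6.1.1 provides that patients whose Day 15 dose has to be omitted "after two dose reductions must be removed from protocol therapy". Two reductions cannot have occurred by Day 15 of Cycle 1.
- Section 5.5 confines the DLT window to Cycle 1 only for dose escalation.
- Section 6.3.1 governs later doses, not only later cycles.

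**Number of doses concerned.** Over *k* cycles there are 2*k* doses, of which *k* - 1 are Day 15 doses after Cycle 1:
- *k* = 2: 1/4 = 25%
- *k* = 3: 2/6 = 33%
- *k* = 6: 5/12 = 42%
- *k* = 13: 12/26 = 46%

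These are shares of doses, not of risk. The documents do not give an expected number of cycles.

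**Age of the last required chemistry at Day 15, Cycles 2-13.** Day 1 to Day 15 is 14 days, and the 72-hour window adds 0 to 3 days.
- Dose on Day 15: 14 + (0 to 3) = 14 to 17 days.
- Dose moved to Day 18 by a hematologic or non-laboratory hold: up to 17 + 3 = 20 days.
- Hold caused by a laboratory toxicity: the 20-day figure does not apply, because recovery cannot be shown without a new result between Day 15 and Day 18.
- Cycle 1, for comparison: about 7 days on the weekly schedule.

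**How far a value must move to meet the rule unseen.** Section 4.1.7.3 limits bilirubin to 1.5 times the "upper limit of normal (ULN) for age regardless of baseline" and ALT to 135 U/L. Appendix IX sets the grades; for ALT it states: "For the purpose of this study, the ULN for ALT is 45 U/L regardless of baseline".
- Bilirubin, reading the multiples in Appendix IX as multiples of ULN: Grade 3 begins above 3 times, so the rise is at least 3/1.5 = 2.0-fold.
- ALT, Grade 4: above 900 U/L, a rise of at least 900/135 = 6.7-fold.
- ALT, Grade 3: from 226 U/L, a rise of 226/135 = 1.7-fold. Section 5.5.1.1 excludes this grade only if it returns to Grade 1 or baseline before the next cycle. That is unknown on Day 15, so the action then is indeterminate. The 6.7-fold figure is therefore firm for Grade 4 only.
- Creatinine and electrolytes: Appendix IX lists no thresholds, so no fold change is computed.

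**How long the exposure lasts.** Section 5.2 rechecks the eligibility laboratory values, and the 8.1 table repeats electrolytes, before each cycle. A persisting event is then found, so normally one Day 15 dose is exposed.

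**The case against.** The strongest defence is that this is a deliberate, risk-based taper. Monitoring is heaviest in Cycle 1. The CBC stays weekly because myelosuppression is the leading expected toxicity. Chemistry is relaxed because nothing in the visible text points to the liver, kidney or electrolytes: Section 2.2.2 expected myelosuppression, GI toxicity, tachycardia and hypotension, and the common adult non-hematologic events in 2.3.1 were mostly Grade 1. Patients reaching Cycle 2 have normally had a cycle with weekly chemistry, and there is no intra-patient escalation. Mean adult half-life at 105 mg/m² ranged from 8.30 to 18.3 hours (2.3.2), so 14 days (336 h) is about 336/18.3 = 18 to 336/8.30 = 40 half-lives. Known toxicity already calls for a repeat test under 6.1.2 and 6.3.1, and sites may test on judgment.

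All of this stands as a reason to rate the point low, and it narrows the gap to a new or recurrent silent event. It does not give the Day 15 rule a scheduled laboratory input. The drug also had no pediatric data when the plan was written (2.4).

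Two further objections are fair. The cycle scope of 6.1.2 is inferred, and the two-reductions wording sits only in the hematologic rule. A 72-hour window is also tighter than the weekly schedule in Cycle 1. It is borrowed from the table's own pre-cycle window; the sponsor may prefer another width, and the point concerns the missing draw.

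A reader might infer that the two sections contradict each other. They do not: 6.1.2 says what to do when toxicity is present and does not promise a screening test.

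**Conclusion.** The point holds as a low-severity matter of patient safety. In Cycles 2-13, at most 12 Day 15 doses per patient, the last required chemistry is 14 to 17 days old, or up to 20 days after a hematologic or non-laboratory hold. A new silent laboratory toxicity that meets 6.1.2 would not be found by any scheduled test before dosing. Exposure is normally limited to one Day 15 dose.

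This rests on two assumptions: that 6.1.2 applies in every cycle, and that no Day 15 chemistry is required elsewhere. Section 9.0 is blank in the public copy, and the roadmaps and CRF packet named in 14.1 are not included, so a requirement there could not be ruled out.

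Three stronger readings are not supported:
- **The MTD or RP2D is compromised.** Escalation uses Cycle 1, when chemistry is weekly.
- **Up to 46% of doses are unsafe.** That is the share of doses without scheduled mid-cycle chemistry. The documents give no event rate from which to derive a risk.
- **The drug is known to cause silent liver, renal or electrolyte injury.** The visible text shows no such signal.

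**What to change.** Add a footnote to the electrolyte row and the creatinine, ALT and bilirubin row of the Section 8.1 table: *In Cycles 2-13, also obtain within 72 hours before the Day 15 infusion, drawn with the weekly CBC, and review before dosing.*

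The last chemistry at Day 15 would then be 0 to 3 days old instead of 14 to 17. If Section 9.0, the roadmaps or the CRF packet already require this test, the footnote simply brings the table into line.

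The cost is *k* - 1 extra samples per patient, at most 12 over 13 cycles, taken with a CBC that is already due, plus some data entry. The documents give no volume per sample. Assuming 1 to 3 ml, the total is 12 to 36 ml over about 12 months, against the 32 to 43 ml of correlative-study blood that Appendix II lists for Cycle 1. One draw finds toxicity still present near Day 15; it does not find an event that rose and resolved earlier in the cycle.
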